Power Analysis: For Aim 1, previous evaluations of BEI report a large effect of treatment on days of alcohol use (d=2.67; Winters et al., 2007). A sample size of 300 (G*Power 3.1.2 software), with alpha of 0.05 for a two-tailed test, will provide power = 0.96 to detect a small treatment effect size of 0.25 if there are no drop outs. Assuming a maximum dropout rate of 15%, as shown in previous studies with Hispanic adolescents with behavior problems (Pantin et al., 2009; Prado et al., 2007), the power drops slightly to 0.90. We also plan to measure the impact of concurrent medication use on treatment effect. For this analysis there are now two groups of participants, those currently using stimulant medication and those not using stimulant medication. The sample size of 300 with a maximum drop-out rate of 15% will provide .90 power to detect an interaction effect of medication, assuming a small pre-test to post-test correlation among measures (r = .25). For Aim 3, a sample size of 150 with a maximum drop-out rate of 15% will provide .90 power for a treatment effect size of .40, which is adequate considering that most ES for similar treatments range between .40 and .80 (Waldron & Turner, 2008). Thus, the sample should be sufficient to detect significant effects of treatment as well possible prediction models.

c. Potential Risks

Risk: Participants may experience mild and transitory psychological discomfort from completing research measures that deal with emotionally laden material, including reporting on illicit drug use and other antisocial or illegal behaviors, which may be uncomfortable for some participants. **Procedure:** We will inform participants of the NIH Confidentiality Certificate prior to collecting any data for the study, which will shield the research data from a subpoena or court order. In addition, participants and their parents will be advised to ask questions of study personnel if confidentiality is of a concern, and to refrain from answering questions that cause them personal distress.

Risk: Participants may face risk as they may experience mild and transitory psychological discomfort from changing their behaviors and attitudes as part of the goals of the brief intervention procedures, or from the material or exercises included in the brief intervention sessions. **Procedure:** We recognize that by targeting a substance using population, initial motivation to participate may be low. However, the psychosocial intervention is designed to address motivational deficits through a combination of motivational interviewing techniques, contingency management, and parent- adolescent negotiation sessions. It is expected that the majority of adolescents will be willing to participate in these activities as attendance will be a means of obtaining additional privileges and freedoms at home. Our Center is experienced at running psychosocial interventions for ADHD adolescents and only therapists who have prior experience working with this population will be employed in the study. We experience very low attrition rates (under 5%) from our clinical and research programs for adolescents. None the less, adolescents can refuse to participate in any session they so choose, and families

may discontinue the study at any time. Efforts will be made to reengage adolescents refusing to attend specific sessions.

Risk: Randomization to the augmented treatment arms for non-responders. **Procedure:** This risk will be addressed through the informed consent/assent process, where parents and children will agree to be assigned to treatment groups. Parents and children are free to withdraw from the study at any time and are not obligated to participate in the treatment group they are assigned to. Withdrawing from this study will not affect any future interactions or their participation in any future clinical services or studies at the CCF.

Risk: Participants may experience adverse events related to medication. **Procedure:** While ADHD medication will not occur for all participants, all participants must be able to tolerate stimulant medication to participate in the study. Therefore, the side effect profile of ADHD medications will be reviewed with families during the consent process. Participants with a documented history of intolerance to all approved ADHD medications will be excluded from the study. All participants will undergo structured assessments of psychiatric comorbidity at baseline as well as medication tolerability which should further reduce the rate of serious adverse events For individuals randomized to the psychosocial treatment and medication arm of the study, height, weight, resting blood pressure and pulse will be collected at each following assessment. All of these procedures should minimize the risk of serious adverse events. Each personal care physician's office has their own procedures for handling emergencies, including a 24 hour on call system. To ensure the safety of all participants, [name] (the study psychiatrist and a board certified child psychiatrist) will be available by pager 24 hours a day during medication phases of the study.

Confidentiality Assurances

In virtually all instances, research data collected in the study will be kept strictly confidential and will not be shared with anyone outside of the research team, including referring schools and care providers. The only exceptions to confidentiality, which will be clearly specified in the consent form, will be for information related to medical emergencies, current child abuse or neglect, or imminent risk of death or serious injury to the participant or others. All research materials will be encoded by a research number and will contain no other identifying information. Written materials will be maintained in locked filing cabinets or storage boxes and computer spreadsheets will be saved in protected files requiring a password for access.

Potential Benefits

There may be considerable potential social, emotional, and behavioral benefits to adolescents who all receive the brief intervention, who may learn new skills to help them reduce or stop their substance use and improve their family and peer relationships. Long term benefits may include a reduced risk for later developing a substance use disorder, or becoming part of the legal system. The relatively small risks to the participants described above are reasonable in light of these potential benefits. The information gained from the study may also help clinicians working with adolescents with ADHD who have comorbid substance use.

Importance of the Knowledge to be Gained

Adolescents with ADHD are a population that is greatly impaired and on track to develop a number of negative outcomes, including substance use and Substance Use Disorder (SUD; Barkley et al., 2004; Charach et al, 2011; Derefinko & Pelham, in press; Lee et al., 2011; Molina, in press; Molina & Pelham, 2003; Sibley et al., 2011). Individuals with ADHD have high rates of substance use across a wide range of substances, including illicit drugs, alcohol, and cigarettes (Arias et al., 2008; Molina & Pelham, 2003; Szobot et al., 2007), and are at risk for early onset of substance use behaviors and disorders (Arias et al., 2008; Milberger et al., 1997; Molina & Pelham, 2003). This proposal represents the first randomized study of brief, early substance use intervention designed specifically for ADHD youth within a sample of clinic-referred adolescents with co-occurring ADHD and emerging substance use. If the proposed treatment is found to be efficacious, it may enhance the long term functioning of the millions of ADHD youth in this country. Information gained from this study concerning behaviors that place adolescents with ADHD at risk for drug use, and how best to intervene with adolescents with these kinds of problems, can assist with developing services for this group, for whom no targeted services are currently available. Given the minimal risk to participants that is incurred by this study, it seems clear that the propensity to gain the above knowledge far outweighs the risks.

Literature Cited

- American Psychiatric Association (2000). Diagnostic and Statistical Manual of Mental Disorders (4th Edition), Text Revision. Washington DC: American Psychiatric Association.

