TITLE: Intervention for Teens with ADHD and Substance Use

- PROTOCOL NO.: DA034731
- **SPONSOR:** National Institute on Drug Abuse
- **INVESTIGATOR:** [name], Ph.D.
- **SITE(S):** Florida International University
- **DATE:** June 4, 2019

ABSTRACT

Individuals with ADHD are at markedly high risk for increased substance use and Substance Use Disorder (SUD; Barkley et al., 2004; Charach et al, 2011; Derefinko & Pelham, in press; Lee et al., 2011; Molina & Pelham, 2003; Sibley et al., 2011). They have high rates of substance use across a wide range of substances, including illicit drugs, alcohol, and cigarettes (Arias et al., 2008; Molina & Pelham, 2003; Szobot et al., 2007), and are at risk for early onset of substance use behaviors and disorders (Arias et al., 2008; Milberger et al., 1997; Molina & Pelham, 2003). Importantly, these substance use problems do not abate over time; among individuals with adult ADHD, rates of substance use disorders approach 40% (Kalbag & Levin, 2005; Biederman et al., 1995), suggesting the need for early intervention. However, treatment of ADHD and substance use concurrently presents a number of problems for clinicians, including poor treatment adherence, lack of treatment progress, and impaired achievement of treatment goals, (Carroll & Rounsaville, 1993; Levin et al., 2004; Wise et al., 2001). Given these barriers, it is clear that future prevention and intervention development should follow the quidelines provided by the current literature on both ADHD and substance use treatment. Several psychosocial interventions for teens with SUD are well-established (Waldron & Turner, 2008; Winters & Leitten, 2007). However, typical studies that have examined efficacy of substance use interventions have conducted only secondary analyses to see if comorbid psychiatric diagnoses moderate outcome. There have been no controlled evaluations of how comorbid ADHD affects the efficacy of early intervention for early substance use. Given the strong evidence for the negative trajectory for individuals with co-occurring ADHD and substance use initiation, our goal is to conduct a controlled examination of a brief. early intervention for substance use (BEI; Teen Intervene, Winters & Leitten, 2007) modified for adolescents with ADHD by using the evidence from both treatment literatures. Importantly, this intervention will address individuals who are at risk for problems with substance use, but do not yet meet criteria for severe SUD. Although brief interventions have been found to be effective in other populations, their efficacy in an ADHD population with emerging substance use remains uninvestigated. We expect BEI to be effective for some but not all ADHD teens, with lower rates of response than have been obtained with nonADHD populations. To better understand why some adolescents with ADHD and elevated risk for substance use problems respond to BEI and others do not, we investigate the contributions of several cognitive, proximal and situational factors to treatment response. Finally, we will randomize non-responders to the BEI to three secondary treatment conditions (monitor only, parent training/adolescent cognitive behavioral therapy, and medication plus parent training/adolescent cognitive behavioral therapy) to determine the relative efficacy of these more intensive interventions for insufficient responders to brief treatment.

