The goal of this study is to evaluate the efficacy of a Brief Early Intervention (BEI) for reducing early alcohol and marijuana use in a group of adolescents (age 12-16) with ADHD who are at elevated risk for substance use problems. All adolescents will receive the BEI (based upon Teen Intervene). The Brief Early Intervention (BEI; 5 individual sessions with adolescent with some parent involvement during 3 of these sessions) will consist of a modification of a brief early intervention program designed by Winters (Winters & Leitten, 2007) with the addition of enhanced decision making skills. Due to the existing support for the intervention, the criterion for eligibility (elevated risk factors for early initiation of substance use), and concern for randomizing families with adolescents at risk for worsening substance use outcomes into a control (no treatment) condition for one to two years, no control condition is used in the current design at the first level of intervention. Similarly, due to the time required to see a potential effect of the treatment (6 months post-brief intervention), a wait-list control condition was not considered.

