The initial part of the study design is to evaluate the effectiveness of the brief early intervention for substance use. Analyses will be based upon measures of substance use and ADHD symptoms, measured at baseline and 6 month assessments. The analytical plan addresses the multiple measurements on the same participant, with a cautious eye toward any concerning missing data issues. We expect drop out to be minimal as has been the case in our decade of experience with treatment studies of ADHD teens. To date, our collective dropout rate is below 5% per year. *Studies conducted in Miami-Dade County with Hispanic adolescents who display behavior problems and emergent substance use report slightly lower retention, with 16-19% attrition (Pantin et al., 2009; Prado et al., 2007). In our studies, data loss has also been relatively low; should there be a missing data issue, we suspect that the last observation carried forward method (LOCF) will be a satisfactory strategy to use. However, we are well aware of other methods and would also use the Mixed-Effects Model Repeated Measures (MMRM) which is more robust to biases and provides better control on type I and II error.*

A careful assessment of data quality will be undertaken as data are being collected and entered, with the usual set of appropriate value, range and logic checks. Data will be collected and handled in a manner that satisfies all local and national requirements for personal privacy, specifically PHI, and data security. Prior to analyzing outcome, comprehensive assessments of data quality, including examination of requirements for the assumptions underlying outcome analyses (i.e., normality, linearity, independence, homogeneity of variance) will be undertaken. Should these assumptions not be met, we will adjust the analytical approach or use transformations as appropriate. We will also apply standard methods for outlier detection (e.g., analysis of leverage statistics, residuals, and df Betas), and use robust statistical significance tests if variance is heterogeneous or re-specify model terms if assumptions of linearity are violated.

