Aim 1: The first aim is to test whether individuals' substance use outcomes decrease significantly from baseline to 6-month assessment. We will calculate days of alcohol and marijuana use during the past 90-days using data from the Substance Use Questionnaire. We will also examine quantity of alcohol use gathered from the SUQ. Repeated measures GLM techniques as implemented by SAS PROC GLM will be used. Several control variables (age, ethnicity, family SES, gender, and functional impairment associated with ADHD) will be entered into the model as covariates. As a secondary analysis, we will also examine % of participants at each

randomization point (6-months, 9 months, 12 months, 15 months, 18 months) who continue to maintain normative use in a time until they stop context. For these analyses, we expect to use Cox Proportional Hazards Regression techniques.

Aim 2: The second aim of this study is to test whether situational, proximal, and cognitive variables listed above predict response to the BEI. At this stage of the study, we will investigate whether each secondary outcome (see Table 5) is a significant predictor of treatment response. Using the GLM as described above, we will investigate the impact of the covariates on substance use variables over time. Predictors will be entered in to the model simultaneously, so long as our sample size adequately supports such inclusion. Should the Cox Regression model, which measures timing, provide a more sensitive measure of substance use trajectories, we will include moderator terms in this model as well.

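### The brief-intervention stage is a single-arm pre-post evaluation, but the protocol describes it as controlled, randomized and a test of efficacy; a 50% response rate could also be reached with no change

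*Combined protocol and SAP*

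**What the plan says.** Under Research Design and Methods, all adolescents get the BEI and "no control condition is used in the current design at the first level of intervention". Three reasons are given: existing support for the intervention, the eligibility criterion of elevated risk, and concern about leaving at-risk teens untreated for one to two years. A wait-list was also ruled out because of the time needed to see an effect. Randomization to the three second-stage conditions happens only after non-response (Research Design and Methods; Follow-up Assessment and Interventions; Analyses, Aim 3).

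Four statements describe the first stage more strongly than that:

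- Research Design and Methods: "The goal of this study is to evaluate the efficacy of a Brief Early Intervention (BEI) for reducing early alcohol and marijuana use".
- Abstract: "our goal is to conduct a controlled examination of a brief. early intervention for substance use".
- Analyses, opening paragraph: "The initial part of the study design is to evaluate the effectiveness of the brief early intervention for substance use".
- Importance of the Knowledge to be Gained: "This proposal represents the first randomized study of brief, early substance use intervention".

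The Aim 1 analysis is a repeated-measures test of whether use falls from baseline to 6 months. Its covariates are age, ethnicity, family SES, gender and ADHD-related impairment. Aim 2 asks which variables predict response, and adds for an optional Cox model that "we will include moderator terms in this model as well".

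Response means no more than normative use at 6 months, and about 50% are expected to respond (Hypotheses and Data Analysis). Under Participants, the teen's own non-normative use is one of six alternative substance-specific risk factors. The others are cigarette or e-cigarette use, parental use, family history, another child in the home using, and perceived peer use.

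**The concern.** A one-arm change from baseline combines any BEI effect with whatever would have happened anyway. The covariates adjust for differences between teens. None of them supplies the untreated time course within a teen, and entering age does not remove six months of ageing. The documents give no external comparator or historical benchmark, and they set no limit on causal reading of the change.

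The response criterion has a separate weakness: it looks only at the 6-month level, not at change. A teen who entered through family history or peer use, and who drinks or uses nothing at intake or at 6 months, is counted as a success of the BEI.

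At stake is the headline result of the first stage. Either a significant fall or a response rate near 50% could be reported as efficacy from a controlled or randomized study when this stage is neither.

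**Working it through.** **1. What is randomized.** The BEI stage has one condition and no allocation. The second stage has three conditions, to which BEI non-responders are allocated. Randomized and controlled therefore describe Aim 3. They do not describe Aims 1 and 2.

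**2. The plan's own power figure.** Inputs from Power Analysis: n = 300, two-sided alpha 0.05, effect size d = 0.25, dropout 15% (300 × 0.85 = 255), stated power 0.96 and 0.90. The pre-post correlation r = 0.25 is stated there only for the medication interaction; applying it to Aim 1 is an assumption.

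Paired t test: dz = d / √(2(1 − r)) = 0.25 / √1.5 = 0.204; noncentrality = dz × √n.

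- n = 300: 0.204 × 17.32 = 3.54, power 0.94 (stated 0.96).
- n = 255: 0.204 × 15.97 = 3.26, power 0.90 (stated 0.90).

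As a 1:1 two-group comparison, the same inputs give about 0.58 and 0.51. The stated power is thus close to that of a pre-post test, and the plan does not contain a controlled comparison under another name.

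**3. What the test would show if the BEI did nothing.** Replace d by an assumed background change, in either direction. The documents give none, so the values below are hypothetical. Entries are the probability of a significant two-sided result at r = 0.25.

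| Background change (SD) | n = 300 | n = 255 |
|---|---|---|
| 0 | 0.05 | 0.05 |
| 0.05 | 0.11 | 0.10 |
| 0.10 | 0.29 | 0.25 |
| 0.20 | 0.80 | 0.74 |
| 0.25 | 0.94 | 0.90 |

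The choice of r matters moderately. For 0.10 SD at n = 300, dz = 0.10 / √(2(1 − r)) gives noncentrality 1.22, 1.41 and 1.73 for r = 0, 0.25 and 0.50, and probabilities of 0.23, 0.29 and 0.41. For 0.25 SD they are 0.86, 0.94 and 0.99.

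**4. Why no sign can be put on the background change.** Regression to the mean is (1 − r) × the sample's mean deviation from its source population. Suppose users are the top third of a normal source population and are enrolled in that same proportion. Their mean is +1.09 SD, the others average −0.545 SD, and (1/3)(1.09) + (2/3)(−0.545) = 0, so net regression is zero. It becomes a net fall only if the sample is enriched for users relative to its source, and the documents do not give that enrichment. Normal theory is also a poor guide to 90-day use counts, because teens at zero can only rise. Rising use with age pushes in the opposite direction to a fall.

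**5. Response without change.** Let u be the share with non-normative use at intake. If nobody changes status, the 6-month response proportion is 1 − u. Any u of 0.50 or less then meets the 50% hypothesis; u = 0.30, for example, gives 70%. The documents do not state an expected u.

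**The case against.** The missing control is disclosed and argued for, and randomization is placed consistently among non-responders. The aims themselves are milder than the surrounding prose. Aim 1 investigates response and tests a fall from baseline, and Aim 2 is worded mainly as prediction, with moderator terms mentioned once as a conditional option. The sentence on the first randomized study stands in a section on expected benefits, in a trial that does randomize. All of this is fair. It makes the point one of stated claims and permitted conclusions, and gives no reason to change the design.

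A reader might go further and infer that regression to the mean would by itself produce the 0.25 SD that Aim 1 is powered to detect, for instance by supposing that a third of the sample enters one SD high. The documents do not support this. They give neither the fraction nor the deviation, r is stated for another analysis, and net regression can be zero. The route through the teen's own use also has no stated time window for self-report, so selection at a temporary high point is an inference.

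What remains is that four statements assign to the first stage a property or a conclusion that it cannot have, and nothing in the analysis plan limits them.

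**Conclusion.** The point holds as a mismatch between design and claims. The BEI stage is uncontrolled, so Aim 1 can describe change and the level of use at 6 months but cannot show efficacy. Bias could run either way. Terms entered in Aim 2 identify who does well after the BEI; without a comparison arm they cannot show for whom the BEI works.

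The size is conditional. With no BEI effect, n = 300 and r assumed to be 0.25, the chance of a significant result runs from 5% with no net background change through about 29% at 0.10 SD to about 94% at 0.25 SD. These figures illustrate how little drift is needed; they do not estimate the drift in this sample. The finding on the response criterion needs no such assumption about drift: it follows from the eligibility rules and the definition of response.

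**What to change.** Keep the design and make these changes:

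- State Aim 1 as uncontrolled pre-post change, plus the 6-month response proportion with a 95% confidence interval.
- Remove controlled and first randomized where they refer to the BEI, and align the efficacy and effectiveness wording with Aim 1 as restated. Reserve efficacy claims for the randomized comparison in Aim 3.
- Treat the moderator terms of the optional Cox model as prognostic predictors.
- Report Aim 1 change and response separately for teens with and without non-normative use at intake. Label the split as descriptive. It conditions on the baseline value of the outcome, so users will tend to fall and non-users to rise, and it cannot by itself separate regression to the mean from a BEI effect. It does show how much of the response rate comes from teens who had no non-normative use to reduce.

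The cost is wording and one extra table from data already collected, with more modest first-stage claims. Adding a control arm at the same size is not proposed. Splitting 300 teens 1:1 would give power of about 0.58 for d = 0.25, and 90% power would need 337 per arm, or 793 in total after 15% dropout (674 / 0.85).
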